7.4. Missing Data and Sensitivity Analysis

Analysis of performance and safety data will be primarily performed on all observed (available) data. Missing data will be summarized, and multiple imputations on missing data may be used for sensitivity analysis to ensure study results are robust.

7.5. Accounting for Multiple Comparisons

There is only one primary hypothesis, therefore, no adjustments for multiple comparisons or multiplicity will be made for this study.

7.6. Interim analysis

There are no planned interim analyses.

8. STATISTICAL ANALYSES

8.1. General Methods

All data collected in this study will be presented using summary tables, figures, and data listings. For categorical data, the number and percentage of subjects in each category will be presented. For continuous data, descriptive statistics, including sample size, mean, median, standard deviation, and range of values (i.e., minimum and maximum values) will be provided.

A significance level of 0.05 will be used for all statistical tests and p-value less than 0.05 will be considered statistically significant unless otherwise specified. The two-sided 95% confidence intervals will be presented whenever appropriate. Statistical analysis will be carried out using SAS software version 9.4 or higher, or other similar validated software.

By-subject listings will be presented for all subjects in the relevant analysis sets.

8.2. Study Subjects

8.2.1. Disposition of Subjects

The disposition of all subjects in the study will be provided for all available data. The numbers of subjects screened, enrolled, completed, and discontinued during the study, as well as the reasons for all post-enrollment discontinuations will be summarized, for all centers combined and for each center separately. Disposition and reason for study discontinuation will also be provided as a by-subject listing.

8.2.2. Protocol Deviation

Protocol deviation will be summarized by category. Protocol deviation data will be listed for each subject. Major protocol violations will be summarized.

8.3. Demographics

Demographic and baseline characteristics are to be summarized. These variables include: age at ICF, and gender.

8.4. Medical History

Medical history data will be summarized and presented by count and percentage of subjects broken down by body systems, Pertinent Past Medical History Conditions, and medical history category as captured on the CRFs. Subjects reporting more than 1 condition within a body system will be counted only once for that body system. By subject listings will be provided for each subject.

8.5. Procedure

Procedure will be summarized and/or analyzed. These variables include details of initial and replacement (if applicable) catheter information, length of tunneling of EVD catheter in the brain, and EVD system and accessories usage.

8.6. Additional information

Additional questionnaires will be summarized using descriptive statistics, and by-subject listing will be provided. Data will be analyzed for the primary and secondary endpoints.

8.7. Concomitant Medications/Procedures

Concomitant Medications and/or Procedures information will be summarized using descriptive statistics by visit, by subject listing will be provided.

8.8. CSF Drainage

Total CSF Drainage volume will be summarized by subject. Data will be listed by catheter by subject.

8.9. Clinical Performance Analyses

All performance analyses will be primarily based on FAS. The Primary and Secondary endpoints analyses will also be performed based on PP.

8.9.1. Analysis of Primary Endpoint

The primary endpoint is anticipated drainage (i.e., observed drainage consisting with the patient's clinical presentation) of cerebrospinal fluid (CSF) in the clinical setting until the EVD System is no longer required.

Note: Excessive drainage (e.g., more than 25 cc every hour) not attributable to the patient's condition, widely variable drainage over time inconsistent with the patient's clinical presentation, drainage levels inconsistent with concurrent neurological exams (e.g., GCS, NIHSS, etc.), and/or documented device deficiencies impacting drainage (e.g., breakage disconnection, etc.) are examples of unanticipated drainage of CSF that will be recorded as Adverse Events.

The primary hypothesis will be tested using the exact (Clopper-Pearson) method along with two-sided 95% confidence interval. The null hypothesis will be rejected, and primary objective will be met if the lower bound of the 95% confidence interval is greater than the performance goal of 80%.

8.9.2. Analysis of the secondary Endpoints

The secondary endpoint is the proportion of patients in whom the CODMAN Cranial Access Kit, when used with appropriate accessories, provided successful access to the intracranial space. The number and percentage of patients with intracranial space success, along with two-sided 95% confidence interval of the percentage will be provided.

8.9.3. Analysis of the tertiary Endpoints

The exploratory endpoints include:

- Number of initial Catheter Insertion Attempts [Time Frame: Implantation of subject] Number of insertions needed to place initial Catheter
- Number of days the initial Catheter is in place.
- Number of Catheter and/or EVD System replacements during treatment, if applicable.
- Number of Catheter flushing interventions per each Catheter if a replacement Catheter is implanted.
- Length of Catheter Tunneling into the Brain [Time Frame: Implant of subject] Length of tunneling of EVD Catheter in the brain for each analysis population.
- Number of Days with initial Indwelling Catheter [Time Frame: Implant of subjects to the day of explant] Days Catheter was implanted in subjects
- Non-infectious Catheter Failure in the intent-to-treat (ITT) Population [Time Frame: Implant of subject to explant] Reasons for non-infectious Catheter malfunctions in the ITT population.
- CSF daily drainage

For categorical endpoints (Number of initial Catheter Insertion Attempts, Number of Catheter and/or EVD System replacements during treatment, Number of Catheter flushing interventions per each Catheter if a replacement Catheter is implanted, Non-infectious Catheter Failure in the intent-to-treat (ITT) Population), frequencies and percentages will be provided for each category. For continuous tertiary endpoints (Number of days initial Catheter is in place, Length of Catheter Tunneling into the Brain, Number of Days with initial Indwelling Catheter, CSF daily drainage), descriptive statistics, including sample size, mean, median, standard deviation, and range of values (i.e., minimum and maximum values) will be provided along with 95% confidence interval of the percentage.

8.10. Safety Analyses

All safety summaries will be presented for the FAS population. No formal statistical testing is planned on safety endpoints.

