11.4.6 Safety Analyses

The safety endpoints of this study are:

- Device- or procedure-related adverse events (AEs) during the use of the device in the patient
- Noted Device Deficiencies during use of the device such as malfunction, use errors, or other issues related to the performance or safety of the External Ventricular Drainage Systems and Accessories

AEs will be coded using the MedDRA terminology for data summaries. Each AE will be coded with 2 levels including Preferred Term (PT) and System Organ Class (SOC).

The total number of EVD system and accessories-related AEs as well as the percentage of patients with at least one device-related AE will be presented overall and by SOC and PT. AEs will also be tabulated by severity and by relationship to EVD system or accessories within each SOC and PT. A listing of EVD system and accessories-related AEs and SAEs will be presented respectively.

The total number of DDs as well as the percentage of patients with at least one DD will be presented overall and by drainage system. A listing of DDs will be presented.

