4.2. Safety Objective

The safety objective of this registry is to capture clinical safety data to confirm the continued safety of the External Ventricular Drainage Systems and Accessories.

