7.2. Determination of Sample Size

A sample size of 110 is estimated by pre-defined performance goal of 80% along with two-sided 95% confidence interval with 80% power for the primary endpoint. A total of 120 subjects will be enrolled with an 8% potential drop-out assumed. The registry will enroll patients who meet the eligibility criteria with an expected total sample size of 120 patients that underwent the procedure with one or more of the Integra devices at up to 15 study sites. Enrollment will be halted at sites that reach the 34% (40 subjects) inclusion cap. There will be no minimum number of subjects for a single study site.

The device systems have been on the market for more than 15 years and have substantial clinical evidence of safety and performance in the form of several peer-reviewed publications and post-market clinical experience data. In this study, data from multiple centers and nations will be included to ensure that the collected data is from a broad set of surgeons and countries, thereby increasing the generalizability of the outcomes and conclusions.

Integra believes this study design and size is appropriate to confirm the continued safety and performance of these devices given their well-established nature and the existing clinical evidence base.

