8.10.1. Adverse Events

All AEs and complications occurring from the time of subject enrollment until study termination or study completion include intra-operative AEs and complications. AEs will be coded using the Medical Dictionary for Regulatory Activities (MedDRA) terminology for data summaries. Each AE will be coded with 2 levels including Preferred Term (PT) and System Organ Class (SOC). The severity of all adverse events will be reviewed and adjudicated and classified as mild, moderate or severe.

The total number of device-related AEs as well as the percentage of patients with at least one device-related AE will be presented overall and by SOC and PT. AEs will also be tabulated by severity and by relationship to device within each SOC and PT. A listing of device-related AEs and SAEs will be presented respectively.

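### The safety objective is worded as confirmation, but no interval, reference rate or precision is specified for any safety percentage; zero events in 110 patients still leaves a 95% upper limit of 3.3%

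*SAP*

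**What the plan says.** SAP 4.2 gives the aim as to "capture clinical safety data to confirm the continued safety of the External Ventricular Drainage Systems and Accessories"; Protocol 3.2 has the same objective. It is one of only two objectives, the other being performance.

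On size, SAP 7.2 states: "Integra believes this study design and size is appropriate to confirm the continued safety and performance of these devices given their well-established nature". The sentence goes on to cite the existing evidence base, and Protocol 11.2 has the same statement. The number itself, 110 evaluable and 120 enrolled, is tied in both places to the primary drainage endpoint and its 80% performance goal.

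On analysis:

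- SAP 8.10: "All safety summaries will be presented for the FAS population. No formal statistical testing is planned on safety endpoints".
- SAP 8.10.1, adverse events: "The total number of device-related AEs as well as the percentage of patients with at least one device-related AE will be presented overall", with breakdowns by system organ class, preferred term, severity and relationship, plus listings.
- Protocol 11.4.6, device deficiencies: "The total number of DDs as well as the percentage of patients with at least one DD will be presented overall and by drainage system". SAP 8.10.2 adds only descriptive statistics and a listing.

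The safety sections name no interval. SAP 8.9.1 and 8.9.2 do name a two-sided 95% interval for the primary and secondary endpoints. SAP 8.1 has a general sentence that such intervals will be shown where appropriate, without tying it to any endpoint.

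**The concern.** Confirming safety implies that the data will show harms to be acceptably infrequent. A bare percentage cannot show that, because it does not say which higher rates remain compatible with the data. The problem is sharpest at zero or one event, where the observed figure looks most reassuring and its uncertainty is easiest to overlook.

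The sizing statement adds to this. It calls the size appropriate to confirm safety, but the calculation behind it involves no safety outcome, and the reasons offered are the devices' market history and prior evidence. Followed as written, the plan would let the report set a low or zero percentage beside the word confirmed without showing what was excluded. For serious but uncommon harms, that could overstate what the registry has learned.

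**Working it through.** **1. Where the sample size comes from.** Inputs: goal 80% and two-sided 95% interval (SAP 7.2), expected success 90% (Protocol 5.5), power 80% and drop-out 8% (SAP 7.2).

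- Normal (score) formula: n = [(1.960·√(0.8·0.2) + 0.842·√(0.9·0.1)) / 0.10]² = 107.4, so 108, close to the stated 110.
- Exact rule at n = 110: the Clopper-Pearson lower bound exceeds 80% from 97 successes upward. Power at a true 90% is 79.1%.
- Drop-out: 110 / (1 − 0.08) = 119.6, so 120.

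The stated size is reproduced, and no safety input enters it.

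**2. What that size delivers for safety.** Inputs: n = 110 (evaluable) and n = 120 (enrolled). Both are shown because the safety set is the FAS, and Protocol 10 keeps data up to withdrawal, so the safety denominator could approach 120.

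For zero events, the exact two-sided 95% upper limit is 1 − 0.025^(1/n):

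- n = 110: 1 − 0.025^(1/110) = 3.30%
- n = 120: 1 − 0.025^(1/120) = 3.03%

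For x > 0 the upper limit is the p that solves P(X ≤ x | n, p) = 0.025. For one event in 110, (1 − p)^110 + 110·p·(1 − p)^109 = 0.025 gives p = 4.96%.

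| Events in 110 | Observed | Exact two-sided 95% upper limit |
|---|---|---|
| 0 | 0% | 3.3% |
| 1 | 0.9% | 5.0% |
| 3 | 2.7% | 7.8% |
| 11 | 10.0% | 17.2% |

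The zero-event row is the best case. A one-sided 95% limit would be 1 − 0.05^(1/110) = 2.7%.

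**3. How often an uncommon harm would not be seen.** The chance of no event in 110 patients is (1 − p)^110. The true rates below are assumptions; the documents give none for this purpose.

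- p = 0.5%: 0.995^110 = 58%
- p = 1%: 0.99^110 = 33%
- p = 2%: 0.98^110 = 11%
- p = 3%: 0.97^110 = 3.5%

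A harm affecting one patient in a hundred would go unseen in about a third of registries of this size.

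**The case against.** Several points on the other side carry weight.

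- **Descriptive safety reporting is normal in a single-arm observational registry.** This stands. A reader might infer that planning no test is itself an error. It is not; the gap is between the word confirm and a descriptive plan with no stated precision.
- **SAP 8.1 already provides for intervals.** A reader might infer that no safety result can carry an upper bound. The documents do not support that, because the general clause could cover safety percentages. But it is discretionary, names no endpoint or method, and does not commit to an interval for zero counts.
- **No document says safety is confirmed whatever is observed.** This stands. A reader might infer that any adverse event or deficiency rate would pass. The documents state no safety decision rule at all, so a rule that always passes, and a probability for it, would be invented. Some provisions also respond to outcomes. Deficiencies impacting drainage are examples of unanticipated drainage under the primary endpoint, which fails at 14 or more failures in 110 (at most 13, or 11.8%, are allowed). Protocol 9.4 treats an inconsistent event frequency as unanticipated, Protocol 9.7.3 provides for ongoing sponsor review, and Protocol 12.1.2 allows suspension for unacceptable risk. None of these sets a numerical limit for harms such as infection or hemorrhage, which need not affect drainage.
- **The sizing sentence leans on prior evidence and does not claim to exclude rare events.** This is fair. It still calls the design and size appropriate to confirm safety without saying how precisely safety will be measured.
- **Safety is not singled out.** This is partly right. Protocol 11.4.5 gives intervals for categorical tertiary percentages, but SAP 8.9.3 attaches its interval wording to the continuous ones. The clear contrast is with the primary and secondary endpoints.

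**Conclusion.** The point holds as a mismatch between a confirming objective and a descriptive safety plan. No interval, reference rate or precision is specified for any safety percentage, and the size is justified by the drainage endpoint alone. The complication rates in the Protocol synopsis are background and are not adopted as safety references.

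At best, with no event of a given type observed, the registry excludes rates above 3.3% (n = 110) or 3.0% (n = 120). One event in 110 moves that limit to 5.0%. These figures assume independent patients with complete safety data and a two-sided 95% level; no threshold near 3% appears in the documents.

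This is an inexpensive improvement to reporting and wording. It leaves the primary analysis untouched and calls for neither a safety test nor more patients.

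**What to change.** 1. **SAP 8.10.1 and 8.10.2, Protocol 11.4.6.** Add exact (Clopper-Pearson) two-sided 95% confidence intervals, including for zero counts, for the percentage of FAS patients with at least one device- or procedure-related adverse event (the endpoint as SAP 5.4 defines it), at least one related serious adverse event, and at least one device deficiency.
2. **SAP 7.2 and Protocol 11.2.** Replace the unqualified claim that the size is appropriate to confirm safety with the precision it gives: zero events in 110 patients excludes a true rate above 3.3%, and one event excludes a rate above 5.0%. The similar sentences in the Protocol synopsis and 5.3 should follow.
3. **SAP 4.2 and Protocol 3.2 (and the synopsis).** Either reword the objective to describe or estimate safety, or keep it and state in SAP 8.10 that the safety conclusion will be expressed as the rate excluded by the upper limit.

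These changes do not create a pass/fail criterion for safety and are not meant to. They make the conclusion show its uncertainty.

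The cost is a few sentences in each document and one extra column in tables already planned. The downside for the sponsor is a less favourable statement about rare harms.

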8.10.1. Adverse Events

All AEs and complications occurring from the time of subject enrollment until study termination or study completion include intra-operative AEs and complications. AEs will be coded using the Medical Dictionary for Regulatory Activities (MedDRA) terminology for data summaries. Each AE will be coded with 2 levels including Preferred Term (PT) and System Organ Class (SOC). The severity of all adverse events will be reviewed and adjudicated and classified as mild, moderate or severe.

The total number of device-related AEs as well as the percentage of patients with at least one device-related AE will be presented overall and by SOC and PT. AEs will also be tabulated by severity and by relationship to device within each SOC and PT. A listing of device-related AEs and SAEs will be presented respectively.

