6.3 Point of Enrollment & Enrollment Period

This is an observational study, and the patients will only provide informed consent to allow use of their data. All consented patients are assigned a study identification (ID) number and screened for eligibility in the study. The study will collect data on each patient from (1) the start of the procedure involving External Ventricular Drainage Systems or Accessories until the EVD System is no longer required for drainage and monitoring of CSF, and (2) in patients who have met all eligibility criteria. Patients eligible for the study are identified and informed consent is obtained prior or after the start of treatment with the devices. In case informed consent is obtained:

- Prior to the start of the treatment with the EVD System and Accessories, the data will be prospectively collected from the implantation procedure until the EVD System is no longer required for drainage and monitoring of CSF.
- After the implantation of the EVD System and Accessories and before the EVD System is no longer required for drainage and monitoring of CSF, the data will be retrospectively collected from the implantation procedure until the point of informed consent and prospectively collected until the EVD System is no longer required for drainage and monitoring of CSF.
- After the EVD System is no longer required for drainage and monitoring of CSF, the data will be retrospectively collected from the implantation procedure until the EVD System is no longer required for drainage and monitoring of CSF.

This registry study is anticipated to have an enrollment period of 25 months.

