8.3 Safety and Other Assessments

- Assessment of events related to EVD system and accessories or procedure
 - Medical records will be reviewed for all events that occurred between index procedure and until the EVD System is no longer required for drainage and monitoring of CSF. See

Section 9.1 for complete definitions and information on assessing and documenting events.

- Assessment of noted Device Deficiencies during use of the EVD system and accessories
 - Medical records will be reviewed for device deficiencies (DD) that were documented that occurred between index procedure and until the EVD System is no longer required for drainage and monitoring of CSF. See **Sections 9.1.3 and 9.7.3** for complete definitions and information on assessing and documenting device deficiencies.

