9.6 Time Period and Frequency for Event Assessment and Follow-Up

As previously described, investigators and/or their staff will review the patient's medical record for events that occurred from device implant until the subject exits the study.

All events will be captured on the appropriate CRF. When possible, signs and symptoms indicating a common underlying pathology should be noted as one comprehensive event (i.e., [possible] influenza instead of chills, fever, and vomiting). The investigator or designee should, to the best of their ability, endeavor to document an outcome/resolution for the event. If no resolution can be found in the medical record, the site will note it as ongoing.

Any medical condition that is present at the time that the subject is screened will be considered as baseline (i.e. medical history and/or conditions) and not reported as an event. However, if the study subject's condition deteriorates at any time during the study, it will be recorded as an event. Any procedures/surgeries should be documented on the Concomitant Neurosurgical and Neuro-interventional Procedures Log from device implant until the until the subject exits the study.

Changes in the severity of an event will be documented to allow an assessment of the duration of the event at each level of severity to be performed. Events characterized as intermittent require documentation of onset and duration of each episode.

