9.7 Event Reporting

All AEs and SAEs information will be collected on all subjects regardless the AE or the SAE is procedure- or device related. AE and SAE recording will start at the point of device implant until the subject exits the study.

Each event must be described as follows in the Electronic Data Capture (EDC) system:

- Event Term: A medically defined diagnosis/symptom. Use the highest level of evidence available.
 - Level 1: Diagnosis
 - Level 2: Symptoms
 - Level 3: Signs
- Event Description: Explain the circumstance of becoming aware of the event, how the subject explained the circumstances surrounding the onset of the event, the underlying cause (the diagnosis), coexisting disease, or other condition or complaint involving the event.
- Event Duration: Document by entering the date of onset (start date) and date of resolution (stop date).
- Event Attribution/Causality: Document causal relationship between event and the investigational product (e.g., causally related, probable, possible, unrelated).
- Event Seriousness: Document as serious or not serious.
- Event Severity: Document as mild (transient and easily tolerated by the subject), moderate (discomfort and interrupts normal activities), or severe (incapacitating with inability to work or do usual activity).
- Treatment: Document as none, medication, hospitalization, surgical, and/or other. Any prescribed medication should be noted in the subject's medical records and transcribed onto the event and Concomitant Medications CRFs. If a surgical or invasive procedure is required for an event, document the procedure on the Procedure Log.
- Outcome: Document as recovered without sequelae, recovered with sequelae, ongoing, death, or other. Events will be followed until a resolution has occurred, until a resolution is no longer expected, the pre-existing condition returns to baseline conditions, or the subject exits the study.

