9.7.1 Event Reporting to Regulatory Authorities

All events will be communicated directly to the Sponsor by the investigator or designee. Event reporting will be collected since the time of implant and reported in the EDC. event information will be collected for all events. Event information will be collected on all patients.

Integra LifeSciences Corporation is responsible for the management of the device vigilance database and shall notify the relevant competent authority of incidents that occurred during the registry study, in accordance with Integra LifeSciences Policies and SOPs, the requirements and all applicable regulations.

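### SAP 8.10.1 starts the adverse event period at enrollment and protocol 9.6 sets baseline at screening, although both can fall after implant; followed literally, either wording can only lower the reported AE rate

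*SAP*

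**What the plan says.** SAP 8.10.1 is the only place in the SAP that states a period for adverse events: "All AEs and complications occurring from the time of subject enrollment until study termination or study completion include intra-operative AEs and complications".

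The protocol gives an earlier anchor in four places:
- 8.3: "Medical records will be reviewed for all events that occurred between index procedure and until the EVD System is no longer required".
- 9.6: staff review the record for "events that occurred from device implant until the subject exits the study".
- 9.7: "AE and SAE recording will start at the point of device implant until the subject exits the study".
- 9.7.1: "Event reporting will be collected since the time of implant and reported in the EDC".

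Enrollment is not tied to implant. Protocol 6.3 allows consent before implant, while the drain is in place, or after it is no longer needed, with retrospective collection back to the implantation procedure. Inclusion criterion 3 (protocol 6.1) provides for patients whose system was removed before enrollment. The note to SAP Table 1 also allows consent after implantation.

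On baseline, protocol 9.6 says: "Any medical condition that is present at the time that the subject is screened will be considered as baseline". Such a condition is "considered as baseline (i.e. medical history and/or conditions) and not reported as an event", unless it deteriorates during the study. Protocol 6.3 places screening after consent: "All consented patients are assigned a study identification (ID) number and screened for eligibility in the study".

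SAP 8.10 presents all safety summaries on the FAS, that is, on every included patient who had a procedure with one of the systems.

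**The concern.** Device- or procedure-related AEs are a stated safety endpoint (protocol 3.6, SAP 5.4). Two rules are anchored to an administrative date, enrollment in one case and screening in the other, when the clinically meaningful start is the implantation. For a patient who consents late, both can put a genuine post-implant complication outside the count while the patient remains in the denominator. The error then runs one way, towards a more favourable safety profile.

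Late consent is not a remote case. Protocol 12.1.1.2 expects patients to be unable to consent before treatment fairly often. A legally authorized representative may consent for them, possibly before implant, so this does not fix how many will be consented late.

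**Working it through.** The documents give no figure on this point, so the check sets the passages side by side by timing of consent.

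**Can enrollment simply mean implant?** No. Inclusion criterion 3 speaks of systems removed before enrollment, so the two dates are distinct in the protocol's own usage.

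**Start of the AE period (SAP 8.10.1 against protocol 8.3, 9.6, 9.7, 9.7.1)**
1. Consent before implant: the SAP period begins no later than the protocol's. Nothing is lost. Because recording starts at implant, there should be no earlier AEs to add.
2. Consent while the drain is in place: post-operative AEs between implant and enrollment are recorded under the protocol but lie outside the SAP period as worded. Intra-operative AEs are expressly included.
3. Consent after the drain is no longer needed: participation is already complete (protocol 10), so every post-operative AE precedes enrollment. Read literally, only the intra-operative AEs remain.

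**Baseline rule (protocol 9.6)**
1. Screening before implant: a condition present then cannot be a complication of the study device. No loss.
2. Screening after implant, complication already resolved: it is not present at screening and stays reportable.
3. Screening after implant, complication still present (for example an infection or hemorrhage of the kind listed in protocol 9.4.1): the baseline sentence says it is not an event, while the implant-based review in the same section and the recording rule in 9.7 say it is. The text conflicts with itself.

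In case 3 the loss would occur when the site enters data, so the SAP 7.4 commitment to analyse all observed data could not recover the event.

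**Direction.** In each comparison the effect is either none or a loss. Neither rule adds an AE that the protocol would not record.

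**Size.** It depends on the share of patients consented after implant and, among them, on the share whose AEs all fall in the affected categories. A patient with one excluded and one counted AE still counts as having an event. The documents give neither share, so no rate is offered.

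**The case against.** The strongest reply is that the SAP plainly intends an implant start, so its sentence is loose drafting. Much supports this:
- SAP 5.4 defines the endpoint as AEs during use of the device. An enrollment start would leave almost nothing to count for patients enrolled after removal.
- SAP 7.4 and 8.1 refer to all observed and all collected data.
- SAP 8.11.1 sets day 0 at placement, counts trial duration from placement and moves some partial AE start dates to the placement date.
- The AE tabulation paragraph in 8.10.1 has no date filter, and the same sentence keeps intra-operative events.

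This stands. A reader might infer that the SAP has adopted a rule excluding pre-enrollment AEs, but the documents do not support that. They support an inconsistent sentence that a programmer could follow.

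On the baseline rule, the reply is that deterioration at any time during the study is an event. Since data collection runs from the start of the procedure (protocol 6.3), a new post-implant complication can itself be read as deterioration. This stands in part: it makes 9.6 ambiguous, not a certain exclusion. It does not remove the sentence that tells a site to treat what is present at screening as baseline. Nor is it certain where such a condition would be entered: SAP 8.4 summarizes medical history, but protocol 8.2 lists no such item.

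Finally, no formal safety testing is planned (SAP 8.10), so no hypothesis test on safety is affected. The AE rate remains a reported endpoint.

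**Conclusion.** The plan is wrong as written on two points of wording, and both should be corrected. The SAP's AE period does not match the protocol's. The protocol's baseline rule conflicts with its own implant-based recording when screening is late. If either wording is followed, AEs of late-consented patients are under-counted against an unchanged FAS denominator. The baseline rule matters more, because changing the SAP would not restore an event that was never entered.

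The size is unknown and may be zero if sites record, and programmers tabulate, from implant. The direction rests on sites recording no AEs before implant, as protocol 9.7 requires.

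Two further inferences are not supported:
- That the primary success rate is inflated as well. Unanticipated drainage is to be recorded as an AE with no screening exception (protocol 3.3), and no passage says that success is derived from AE records.
- That events at drain removal are generally lost. The end-of-period mismatch (protocol 8.3 stops when the system is no longer required, 9.7.3 at explant) concerns device deficiencies, and 9.7.3 runs to the explant date. It is at most a minor point to reconcile.

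**What to change.** 1. SAP 8.10.1: replace the enrollment start with the start of the EVD implantation procedure, whatever the consent date.
2. Protocol 9.6: define baseline as conditions present before the start of the implantation procedure.
3. Minor: align the end of the device-deficiency review in protocol 8.3 and 9.7.3.

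Cost: one SAP edit, a small protocol amendment, and a re-check of AE entries for patients already enrolled after implant, in case a complication was entered as baseline. No new analysis is needed. The reported AE rate may turn out less favourable.
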